#### 4.4.1 Available data

Blood samples will be collected for the determination of anti-drug antibodies (ADA) to efgartigimod (in serum samples) and antibodies against rHuPH20 (in plasma samples, only analyzed in case of safety concerns and not in scope of this analysis) at the time points indicated in the schedule of activities (see section 9.2).

SGS	Statistical Analysis Plan	
ARGX-113-1905	Final analysis	Final 1.0 of 26APR2024

[figure not shown]
Immunogenicity samples are analyzed in a 3-tiered approach:

[figure not shown]
- All samples are evaluated in the ADA screening assay and are scored ADA screening positive or negative.
- If a sample scored positive in the ADA screening assay, it is further evaluated in the confirmatory assay and is scored confirmed positive (positive immunodepletion) or confirmed negative (negative immunodepletion).
- If a sample is scored as confirmed positive, the samples are further characterized in the ADA titration assay (to determine titer) and are also further analyzed in the NAb assay to confirm neutralizing activity. For NAb against efgartigimod, a screening assay is performed and results will be reported as negative or positive.

If available, a titer result will be reported for the ADA confirmed positive samples. However, a titer result is not always available:

- In case the ADA confirmed positive sample could not be run in the titration assay (e.g. due to insufficient sample volume/quality to perform the titer analysis), the result will be described as 'positive immuno-depletion' and the sample should be considered as ADA positive.
- If a sample is negative in the titration assay, it will be reported as 'negative titer' but it should be considered as ADA positive since it was confirmed positive in the second tier.
- If a sample could not be analyzed or reported as 'positive screen', the ADA sample status is ADA unevaluable

[figure not shown]
An overview of this 3-tiered approach and all possible ADA sample results that will be reported by the laboratory is presented in Figure 1. From these reported ADA sample results a final ADA sample status needs to be derived during the statistical analysis, as presented in the final column ('Final ADA Outcome'):

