- a missing screen includes the following terms (reported as reason not done): NA (not analyzed), NR (no result), NS (no sample) and SL (sample lost). More details can be found in the IS data transfer agreement (DTA) from LGC (for ADA against efgartigized) with SGS SDO.
- b 'positive titer' is reported in case it was not possible to retrieve a numeric value.

Page 45 of 84

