#### 4.4.2 Derivation rules

#### 4.4.2.1 PARTICIPANT CLASSIFICATION FOR ADA AGAINST EFGARTIGIMOD-OVERALL

Table 6 below gives an overview of how the ADA participant classification will be derived, starting from the participant baseline ADA sample status.

Participant	Highest c post-baseline d sample status				
ADA classification	ADA negative	ADA positive (missing titer a )	ADA positiv titer b or posi numeric ti	itive titer or	ADA not evaluable
Baseline ADA sample status					
ADA negative	ADA negative	Treatment- Induced ADA	Treatment-In	nduced ADA	ADA unevaluable
ADA positive (missing titer a )	Treatment- Unaffected ADA	ADA unevaluable	ADA une	waluable	ADA unevaluable
ADA positive (negative titer b or positive titer or numeric titer value)	Treatment- Unaffected ADA	ADA unevaluable	titer < 4 x baseline titer: Treatment- Unaffected ADA	titer ≥ 4x baseline titer: Treatment- Boosted ADA	ADA unevaluable
ADA not evaluable	ADA unevaluable	ADA unevaluable	ADA une	waluable	ADA unevaluable

Table 6: Participant classification for ADA against Efgartigimod

a Samples with missing titer have as reported ADA result 'positive immunodepletion'or 'positive titer';

b Results reported as 'negative titer', i.e. titer value <1 will be set to value of 1;

c Highest sample status, with order: (from low to high): ADA unevaluable, ADA negative, ADA positive (missing titer /positive immunodepletion), ADA positive with titer <= 1 ('negative titer' as reported ADA result, titer value set to 1), ADA positive with titer >1 (i.e. numeric titer and selecting the sample with highest titer)

d For the overall ADA participant classification, the highest post baseline sample status is used for comparison with the baseline ADA sample status.

ADA evaluable participant = participant classified as any of following categories: ADA negative, treatment-unaffected ADA, treatment-induced ADA, treatmentboosted ADA. The first 2 categories are classified as 'ADA negative', the latter 2 as 'ADA positive'.

ADA unevaluable participant = participant classified as ADA unevaluable or with missing baseline ADA sample or without post-baseline ADA samples.

Note: Fourfold difference in titer values is considered significant in case a twofold serial dilution is applied (= 2 times the dilution factor) (reference to Shankar et al., 2014).

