ADA incidence = percentage of participants with treatment-induced or treatmentboosted ADAs (denominator: number of evaluable participants).

SGS	Statistical Analysis Plan	
ARGX-113-1905	Final analysis	Final 1.0 of 26APR2024

ADA prevalence = percentage of participants with treatment-unaffected ADA, treatment-induced ADA or treatment-boosted ADA (denominator: number of evaluable participants).

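### ADA prevalence leaves out participants known to be ADA positive at baseline and afterwards when the titer comparison cannot be made, so any such participant makes the reported figure too low

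*SAP*

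**What the plan says.** Protocol Section 3 lists incidence and prevalence of ADA against efgartigimod as a secondary endpoint. SAP 4.4.2.1 defines prevalence as "ADA prevalence = percentage of participants with treatment-unaffected ADA, treatment-induced ADA or treatment-boosted ADA (denominator: number of evaluable participants" and incidence as "ADA incidence = percentage of participants with treatment-induced or treatmentboosted ADAs (denominator: number of evaluable participants". Both therefore share one denominator. The participants outside it are given by "ADA unevaluable participant = participant classified as ADA unevaluable or with missing baseline ADA sample or without post-baseline ADA samples".

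On samples, SAP 4.4.1 says that when a confirmed-positive sample could not be run in the titration assay, "the result will be described as 'positive immuno-depletion' and the sample should be considered as ADA positive".

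Table 6 then classifies each participant by baseline status against the highest post-baseline status. Footnote c ranks a positive sample without a titer above a negative one but below any positive with a titer.

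On the label 'positive titer', the notes to Figure 1 say that it "is reported in case it was not possible to retrieve a numeric value". Table 6 footnote a begins "Samples with missing titer have as reported ADA result" and then names positive immunodepletion and 'positive titer'. The Table 6 headings for titered positives nevertheless list 'positive titer' beside negative and numeric titers. Footnote c does not name it.

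**The concern.** Prevalence asks whether ADA are present. Table 6 asks more: whether ADA present at baseline rose at least fourfold under treatment. Failing the second question removes a participant from the answer to the first, even though the first is settled.

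The result is inconsistent. A baseline-positive participant who later tests negative counts as prevalent. A participant positive on both occasions is dropped if the titers cannot be compared. Only known positives are lost by this route, so the error runs in one direction.

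The baseline-positive rows matter in this trial because the 1905 baseline is the roll-over visit (SAP 2.2.3). Participants randomized to efgartigimod in 1904 reach it after earlier exposure.

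**Working it through.** The plan states no ADA rate, missing-titer rate or target for this endpoint, so there is no planned figure to reproduce. The check has three steps.

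**Step 1. Read the cells of Table 6 that involve a positive baseline.**

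| Baseline sample | Highest post-baseline status | Table 6 class | In prevalence? |
|---|---|---|---|
| Positive, no titer | Negative | Unaffected | Yes |
| Positive, no titer | Positive, no titer | Unevaluable | **No** |
| Positive, no titer | Positive, titered | Unevaluable | **No** |
| Positive, titered | Negative | Unaffected | Yes |
| Positive, titered | Positive, no titer | Unevaluable | **No** |
| Positive, titered | Positive, below 4× baseline | Unaffected | Yes |
| Positive, titered | Positive, at least 4× baseline | Boosted | Yes |

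In each of the three excluded cells the true class is either unaffected or boosted. Both are in the prevalence numerator, so the missing titer cannot change prevalence status. For incidence it can, because only boosted counts there.

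**Step 2. Direction.** Let N be the number of participants whose prevalence status is known, a the number of those who are positive, and k the positives in the excluded cells.

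- Prevalence with everyone of known status: a/N
- Prevalence under the SAP: (a−k)/(N−k)
- Difference: (a−k)/(N−k) − a/N = −k(N−a)/[N(N−k)]

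This is negative whenever k>0 and a<N, and zero when k=0.

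**Step 3. Illustrative size.** N = 213 is the maximum in SAP 1.3 and serves only as a scale. The immunogenicity analysis uses the Safety analysis set, which may be smaller. Both a and k are assumed.

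| a | a/N | k | (a−k)/(N−k) | Difference (percentage points) |
|---|---|---|---|---|
| 21 | 9.9% | 0 | 21/213 = 9.9% | 0 |
| 21 | 9.9% | 1 | 20/212 = 9.4% | −0.4 |
| 21 | 9.9% | 3 | 18/210 = 8.6% | −1.3 |
| 21 | 9.9% | 5 | 16/208 = 7.7% | −2.2 |
| 21 | 9.9% | 10 | 11/203 = 5.4% | −4.4 |
| 43 | 20.2% | 5 | 38/208 = 18.3% | −1.9 |
| 106 | 49.8% | 10 | 96/203 = 47.3% | −2.5 |

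Check of the formula at a=21, k=5: 5 × 192 / (213 × 208) = 960/44,304 = 2.2 points.

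For contrast, take incidence with an assumed 15 induced or boosted participants and k=5. The SAP gives 15/208 = 7.2%. The value with all 213 lies between 15/213 = 7.0% and 20/213 = 9.4%, depending on how many of the five were boosted. Incidence is thus truly undetermined for these participants; prevalence is not.

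**The case against.** The best defence is that one set of mutually exclusive categories with one denominator is simple, prespecified and transparent. SAP 4.4.3 tabulates the unevaluable participants and lists all ADA data with sample status and classification, so a reader could recompute prevalence. The analysis is descriptive, with no hypothesis test (protocol 9.2). All this is true and limits the consequence, but disclosure does not correct the percentage printed in Table 14.2.4.2. Nor is it only a matter of preference: SAP 4.4.2.2 counts participants who are NAb positive at baseline and afterwards directly in NAb prevalence, with no titer needed.

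Several stronger readings are tempting, and the documents do not support them:

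- **That 4.4.1 and Table 6 contradict each other.** Section 4.4.1 sets the status of a sample; Table 6 classifies participants and respects that status elsewhere. An untitered positive after a negative baseline, for example, is treatment-induced. The fault lies in carrying the unevaluable class into prevalence.
- **That any untitered later sample removes a participant with a titered positive baseline.** By footnote c, one titered post-baseline positive restores evaluability, and samples are taken every 4 weeks on treatment. The route needs every later positive to lack a titer. A missing baseline titer with any later positive always triggers the exclusion.
- **That the losses are persistently positive participants.** One baseline and one later positive sample are enough.
- **That the result turns on how 'positive titer' is programmed.** The two placements give the same class except where a fourfold ratio is needed, and there no number exists to form one. Footnote a assigns the label to missing titer, and footnote c's titered ranks leave no place for it. What remains is an inconsistent label.

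**Conclusion.** The point holds in a conditional form. The shared evaluability rule discards information that is sufficient for prevalence, and the reported figure is too low if at least one participant falls in the three excluded cells and prevalence is below 100%. One might infer that the reported prevalence will certainly be biased, or by a stated amount. The documents support neither, because the number of such participants may be zero and every count in the illustration is assumed.

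Incidence is not at fault: the unevaluable class is a defensible choice there. The matter is minor, since it concerns a descriptive secondary endpoint and the loss is visible in the planned tables. It is still worth correcting because the direction is known and the remedy is specific.

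**What to change.** In SAP 4.4.2.1:

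1. For prevalence, count every participant with a confirmed-positive baseline sample and a confirmed-positive post-baseline sample in numerator and denominator, whatever the titer. A practical way is a separate Table 6 category, for example 'ADA positive, boosted/unaffected undetermined'.
2. Keep the titer-based unevaluable rule for incidence only.
3. Keep the new category out of the SAP's two-way grouping of participants. That grouping puts unaffected under ADA negative and boosted under ADA positive, and these participants could belong to either.
4. Remove 'positive titer' from the titered row and column headings of Table 6, so that it is a missing titer throughout as footnote a says, and name it in the footnote c ranking.

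The cost is a few sentences, one added category in Table 6 and in the SAP 4.4.3 tabulations by participant category, and two label edits. No new data are needed. The drawback is that incidence and prevalence will have slightly different denominators, which a footnote to Table 14.2.4.2 should state.

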#### 4.4.2.2 PARTICIPANT CLASSIFICATION FOR NAB AGAINST EFGARTIGIMOD-OVERALL

All ADA confirmed positive samples will also be evaluated in the NAb assay. All samples that were not analyzed in the NAb assay (i.e. the ADA negatives) are per default NAb negative. Also, if a NAb sample is not reported, the NAb sample status is NAb unevaluable.

For NAb against efgartigimod, all samples evaluated in the NAb assay will be scored as NAb positive, NAb negative or NAb unevaluable by the laboratory. Based on these results, the participants will be categorized based on their baseline and post-baseline sample status as detailed in table 7.

Participant NAb classification		Highestª post-baseline NAb sample status	
	NAb negative	NAb positive	NAb not evaluable
Baseline NAb sample status			
NAb negative			NAb unevaluable
NAb positive	baseline neg – post- baseline neg baseline pos – post- baseline neg	baseline neg – post- baseline pos baseline pos – post- baseline pos	NAb unevaluable
NAb not evaluable	NAb unevaluable	NAb unevaluable	NAb unevaluable

Table 7: Participant	classification	for NAb	against E	fgartigimod

Highest sample status in order: (from low to high): NAb unevaluable, NAb negative, NAb positive.

For the overall NAb participant classification, the highest post baseline sample status is used for comparison with the baseline NAb sample status.

NAb unevaluable participant = participant classified as NAb unevaluable or with missing baseline NAb sample or without post-baseline NAb samples.

NAb incidence = percentage of participants with participant classification 'baseline neg – post-baseline pos' and 'baseline pos – post-baseline pos' (denominator: number of evaluable participants).

NAb prevalence = percentage of participants with participant classification 'baseline neg – post-baseline pos', 'baseline pos – post-baseline pos' or 'baseline pos – post-baseline neg' (denominator: number of evaluable participants).

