#### 4.4.3 Presentation of results

Frequency tabulations (number and percentages) will be provided with ADA negative/positive/unevaluable samples per analysis visit. In addition, these tables will be repeated by ADA participant category.

SGS	Statistical Analysis Plan	
ARGX-113-1905	Final analysis	Final 1.0 of 26APR2024

Frequency tabulations (number and percentages) will be provided overall on:

- participants per ADA participant category
- prevalence and incidence of ADA
- ADA unevaluable participants
- ADA baseline positive/negative samples

[figure not shown]
For details on the definitions, see the above section 4.4.2.1.

The above frequency tabulations will be repeated for NAb assay using the definitions as defined in section 4.4.2.2.

In addition, a cross-tabulation (number and percentages) will be provided of the overall NAb participant category (NAb positive participants and NAb not evaluable participants) versus the overall ADA participant category (treatment-unaffected ADA, Treatment-induced ADA, Treatment-boosted ADA, ADA Negative, ADA Unevaluable, Total).

ADA titer values against efgartigimod will be summarized by means of descriptive statistics by the ADA participant classification.

All available data on ADA and NAb against efgartigimod will be listed, showing also the sample status and participant classification.

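### SAP 4.4.2.2 labels as NAb incidence any post-baseline NAb positivity among evaluable participants, including those already positive at roll-over

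*SAP*

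**What the plan says.** SAP section 4.4.2.2 cross-classifies each participant by baseline NAb status and highest post-baseline NAb status. The incidence rule is "NAb incidence = percentage of participants with participant classification 'baseline neg – post-baseline pos' and 'baseline pos – post-baseline pos", and its denominator is all evaluable participants. Prevalence uses the same two classes plus baseline positive, post-baseline negative. On evaluability the section says: "NAb unevaluable participant = participant classified as NAb unevaluable or with missing baseline NAb sample or without post-baseline NAb samples". Baseline is the roll-over visit (SAP section 2.2.3).

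For ADA, SAP section 4.4.2.1 says "ADA incidence = percentage of participants with treatment-induced or treatmentboosted ADAs". Under Table 6, a participant with a usable baseline titer is treatment-boosted only if the post-baseline titer is at least four times baseline. Below that, the participant is treatment-unaffected. Of the four evaluable ADA categories (negative, treatment-unaffected, treatment-induced, treatment-boosted), the section says: "The first 2 categories are classified as 'ADA negative', the latter 2 as 'ADA positive".

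On the NAb assay, SAP section 4.4.1 says: "For NAb against efgartigimod, a screening assay is performed and results will be reported as negative or positive". No NAb titer is described.

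SAP section 4.4.3 repeats the ADA frequency tables for NAb. It also plans a cross-tabulation by ADA category of the "overall NAb participant category (NAb positive participants and NAb not evaluable participants").

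**The concern.** A reader takes incidence to mean something that arose or increased after baseline. The SAP applies that idea to ADA but not to NAb. A participant who enters with neutralizing antibodies and still has them later is counted as a NAb incident case, although nothing in the data shows a rise.

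This can occur in an extension study. Participants randomized to efgartigimod in 1904 arrive already exposed (Protocol section 2.1), so a NAb that appeared in 1904 can be present in the roll-over sample. If it persists, it is reported as incident in 1905.

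What is at stake is the label on one percentage in Table 14.2.4.4 and its comparability with the ADA incidence in Table 14.2.4.2. I found no text in either document that explains the different treatment of baseline-positive participants.

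**Working it through.** There is no stated figure to reproduce, so the check applies the definitions to every possible class.

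**1. NAb classes.** Among evaluable participants, let a = negative then positive, b = positive then positive, c = positive then negative, d = negative then negative, and N = a + b + c + d.

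| Baseline | Highest post-baseline | Count | In SAP incidence | In SAP prevalence |
|---|---|---|---|---|
| negative | negative | d | no | no |
| negative | positive | a | yes | yes |
| positive | negative | c | no | yes |
| positive | positive | b | yes | yes |

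The classes are mutually exclusive, so the word joining the two incidence classes can only mean their union. Any combination with an unevaluable baseline or post-baseline status is outside N. That includes a participant with a missing baseline sample and a later positive one.

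**2. Formulas.**
- SAP incidence = 100 × (a + b) / N, which is the percentage with any positive post-baseline sample.
- SAP prevalence = 100 × (a + b + c) / N. It differs from SAP incidence only by c.
- New NAb only = 100 × a / N, or 100 × a / (a + d) among baseline-negative participants.
- Excess of SAP incidence over new NAb, both over N = 100 × b / N.

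**3. Same participant under both rules.** Take someone who is ADA-positive with a titer and NAb-positive at roll-over, and both again later, with a titer below four times baseline.
- ADA (4.4.2.1): treatment-unaffected, grouped as ADA negative, counted in prevalence and not in incidence.
- NAb (4.4.2.2): positive then positive, counted in incidence.

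So the two incidence measures treat baseline-positive participants differently, and NAb incidence could exceed ADA incidence.

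**4. Size per participant.** SAP section 1.3 gives at most about 213 participants. One positive-then-positive participant adds at least 100 / 213 = 0.47 points in the Total column. The step is larger in the prior-treatment columns, which have fewer participants.

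**5. Illustration with assumed counts** (none come from the documents): N = 100, a = 5, c = 2.

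| b | SAP incidence | New NAb over N | New NAb over baseline-negative |
|---|---|---|---|
| 0 | 5% | 5% | 5/98 = 5.1% |
| 2 | 7% | 5% | 5/96 = 5.2% |
| 5 | 10% | 5% | 5/93 = 5.4% |
| 10 | 15% | 5% | 5/88 = 5.7% |

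The SAP figure moves one for one with b, while the new-NAb figure over N does not move.

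**The case against.** The best defence is that the rule is explicit, can be programmed without ambiguity, and hides nothing. Participant category counts are planned for NAb (SAP section 4.4.3). Table 14.2.4.3 shows sample status by visit within each NAb category, and all NAb results are listed with their classification. The negative-to-positive figure can therefore be recovered. Table 14.2.4.4 has no topline flag (SAP section 8.1), no hypothesis is tested (Protocol section 9.2), and the protocol's immunogenicity endpoint names ADA only (Protocol section 3). All of this stands, and it keeps the point minor. It does not make the label correct.

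A second defence is that, without a titer, counting all positive-then-positive participants stands in for the boosted class. This fails as a justification, because a result that is only positive or negative cannot show a boost.

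The same fact limits the criticism. A reader might infer that these participants are unchanged since baseline. The documents do not support that: the class mixes NAb that persisted, NAb that rose, and NAb that disappeared and re-emerged, because the highest post-baseline status is used. The supportable statement is that they are not shown to have changed.

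A reader might also infer that the SAP's own standard for incidence is new antibody only. It is not, since ADA incidence includes treatment-boosted participants.

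Finally, a reader might see a fault in the different evaluable denominators for ADA and NAb. Each section defines its own, and ADA evaluability can require a titer comparison that NAb does not need, so the difference is not a defect.

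**Conclusion.** Wrong as written, and minor. As defined, NAb incidence is post-baseline NAb positivity among NAb-evaluable participants. It includes those already positive at roll-over with no evidence of a rise, and it does not match the ADA rule for baseline-positive participants.

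The excess over new NAb is exactly the positive-then-positive share of evaluable participants. The documents give no NAb rates, so that share is unknown and may be zero. The conclusion about the definition needs no assumption about rates; the illustrative table does.

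It would be tempting to say that the reported NAb rate will be materially inflated, or to grade the problem by counting how many ADA-by-NAb combinations are affected. Neither is supported. Combinations are not participants, and sorting them by ADA class depends on which titers count as missing. Table 6 is unclear on that: a result reported as positive titer appears both under missing titer (footnote a) and in the row and column for available titers. No test, topline result or protocol-named endpoint is affected.

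A separate clarity gap is that section 4.4.2.2 never says which NAb classes make a participant NAb-positive for the cross-tabulation in section 4.4.3.

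**What to change.** In SAP section 4.4.2.2 and Table 14.2.4.4:
- Relabel the current percentage as post-baseline NAb positivity (evaluable participants).
- Report the negative-to-positive class separately as NAb incidence. State its denominator: either all NAb-evaluable participants, which parallels ADA, or those who were NAb-negative at baseline.
- Keep the positive-then-positive class as its own row.
- In section 4.4.3, state which NAb classes make up the NAb-positive participants in the cross-tabulation.

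The cost is SAP wording and one table layout, with no new data. The downside is that a true NAb rise in a baseline-positive participant would not count as incident. This includes someone with treatment-boosted ADA, who would be ADA-incident but not NAb-incident. Such a participant stays visible in the positive-then-positive row and inside the relabelled percentage.
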